8.4 Vital Signs

Vital signs include body temperature, pulse rate, respiratory rate and blood pressure taken in a sitting position at rest for 5 minutes, and are measured at Visit 1 (Screening), Visit 2, Visit 5, Visit 8 EoT/WD, and Visit 9.

Summary of actual values and changes from baseline will be presented for each assessment time point.

The number and percentage of subjects with marked abnormalities post-baseline will be tabulated for each vital sign marked abnormality category. In the listings, the marked abnormalities are classified as high (H, HH) or low (L, LL) based on values occurring above the higher limit or below the lower limit, respectively. Only the most severe abnormality will be counted (e.g. a subject meeting the 'HH' criterion for a specific parameter will not be summarized under 'H' for this parameter. Percentages will be based on the number of subjects at risk for the parameter: those not meeting the criterion at baseline (or having a missing baseline value) and having at least one post-baseline value. The vital signs marked abnormality categories are presented in the table below.

Table 4 Marked abnormalities for vital signs

Parameter (unit)	Abnormality
Weight (kg)	Decrease from baseline > 7% (L flag)
	Increase from baseline > 7% (H flag)
Body temperature (C)	< 36 (L flag)
	> 38 (H flag)
Pulse rate (beats/min)	< 60 (L flag)
	> 100 (H flag)
Respiratory rate (breaths/min)	< 12 (L flag)
	> 20 (H flag)
Systolic blood pressure (mmHg)	< 90 (L flag)
	> 140 (H flag)
	> 160 (HH flag)
Diastolic blood pressure (mmHg)	< 50 (L flag)
	> 90 (H flag)
	> 100 (HH flag)

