6.1 Inclusion Criteria

For inclusion in the trial patients must fulfill ALL of the following criteria:

- 6.1.1 Male or female aged 6 to 17 years (inclusive).
- 6.1.2 Patient weight is at least 12 kg.
- 6.1.3 Patients (if possessing adequate understanding, in the investigator's opinion) and their parent(s)/legal representative are willing and able to give informed consent for participation in the trial.
- 6.1.4 Patient is/and their caregiver are willing and able (in the investigator's opinion) to comply with all trial requirements.
- 6.1.5 Patient has a diagnosis of ASD as per DSM-5 criteria for ASD, confirmed by ADOS-2 criteria (conducted within 2 years at the trial site or at screening by a qualified assessor). Note: During special circumstances (e.g., COVID-19 pandemic) where the ADOS-2 cannot be performed due to site restrictions (e.g., mandatory use of face masks) and an ADOS-2 conducted within 2 years at the trial site by a qualified assessor is not available, eligibility can be confirmed using: 1) an ADOS-2 performed within 2 years by a qualified assessor external to the site; 2) if 1) is not available, eligibility may be confirmed using the ADI-R at screening.
- 6.1.6 CGI-S \geq 4 (moderately ill) at screening and randomization.
- 6.1.7 ABC-I subscale score \geq 15 at screening.
- 6.1.8 IQ \geq 70 at screening, measured within 1 year of screening, using WASI-II.
- 6.1.9 All medications or interventions (including psychosocial interventions, dietary supplements, probiotics, speech therapy, etc.) for ASD related symptoms must have been stable for 4 weeks prior to screening and randomization, and the patient/caregiver should be willing to maintain a stable regimen throughout the trial.
- 6.1.10 Patient must have the ability to swallow the IMP provided as a liquid solution.
- 6.1.11 Patient and/or parent(s)/legal representative is willing to allow the responsible authorities to be notified of participation in the trial, if mandated by local law.
- 6.1.12 Patient and/or parent(s)/legal representative is/are willing to allow the patient's primary care practitioner (if they have one) and consultant (if they have one) to be notified of participation in the trial if the primary care practitioner/consultant is different from the investigator.

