3.1 Design Overview

This is an exploratory, Phase 2, double-blind, randomized, placebo-controlled, multisite trial, which will compare the safety and efficacy of a 10 mg/kg/day dose of GWP42003-P versus placebo in children and adolescents with ASD.

Approximately 160 subjects who meet eligibility criteria and consent to participate in the study are randomly assigned in a 1:1 ratio to one of the following treatment groups:

- GWP42003-P
- Placebo

Patients will be stratified based on their age (6 to 11, 12 to 17), use of antipsychotics (on versus off), and region (North America versus Rest of the World). Patients will be administered 5 mg/kg/day GWP42003-P or matching volumes of placebo for 1 week and then 10 mg/kg/day GWP42003-P or matching volumes of placebo for 11 weeks. At the end of treatment, patients will taper the medication over 1 week.

Overall trial design is outlined in Figure 1.

[figure not shown]

[figure not shown]
Figure 1 Trial Design and Treatment Schematic

Eligible patients may be randomized 7 to 14 days after the screening visit (Visit 1), once all required assessments have been completed and laboratory results have been reviewed; if required, screening assessments may be split over 2 visits; however, both visits must fall into the 7 to 14 day window prior to randomization (Visit 2). One week and 2 weeks following randomization, there will be 2 safety telephone visits (Visit 3 and 4). The patient will return to the clinic or video call and home nurse visit, 4 weeks after randomization (Visit 5). Six weeks after randomization, there will be another safety call (Visit 6), and then the patient will return for a clinic visit or video call visit (Visit 7) 8 weeks after randomization. The end of treatment visit will take place 12 weeks after randomization (Visit 8). If at any point it is decided to withdraw a patient from the trial, the patient should return to the clinic as soon as possible and complete Visit 8 procedures. At Visit 8, patients will commence to taper the medication (unless in case of withdrawal the medication was already discontinued or continued dosing is inadvisable, e.g., due to an AE). At the end of taper, the patient will return to the clinic or video call and home nurse visit (Visit 9). All patients will have a follow-up safety telephone visit, 14 days after Visit 9 or Visit 8 (in case the patient did not taper the medication).

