3.2 Sample Size

3.3 Treatment Randomization

A permuted block randomization scheme was created to assign subjects in a 1:1 ratio to either of the two treatment groups. The scheme was stratified by age (6 to 11 years; 12 to 17 years), use of anti-psychotics (on; off), and region (North America; Other). At visit 2, randomization will be performed for each consenting eligible subject using

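### SAP Table 4 sets one fixed limit each for pulse, respiratory rate and blood pressure for all children aged 6 to 17, which risks a noisy and insensitive vital-sign table in the younger ones

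*SAP*

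**What the plan says.** Protocol section 6.1 admits children and adolescents from 6 to 17 years. SAP sections 3.1 and 3.3 stratify the 1:1 randomization at 6-11 and 12-17 years. Vital signs are a named safety endpoint (Protocol section 2, SAP Table 1).

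SAP section 8.4 tabulates the number and percentage of subjects with a marked abnormality after baseline. The criteria are introduced with "The vital signs marked abnormality categories are presented in the table below". Table 4 then gives:

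- Pulse: below 60 or above 100.
- Respiratory rate: below 12 or above 20.
- Systolic pressure: below 90, above 140 (H) or above 160 (HH).
- Diastolic pressure: below 50, above 90 (H) or above 100 (HH).
- Weight: a change of more than 7% from baseline. This row is relative to the child and is not part of this point.

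The four absolute rows carry no age, sex or height qualifier, and no reference is given for them. The denominator rule is: "Percentages will be based on the number of subjects at risk for the parameter: those not meeting the criterion at baseline". A child with a missing baseline value also counts as at risk, and at least one post-baseline value is required.

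The same section also plans output that does not depend on the limits: "Summary of actual values and changes from baseline will be presented for each assessment time point". In the visible SAP text, age group is a demographic variable (section 6.3.2), and no vital-sign output is shown by age group.

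**The concern.** A marked-abnormality table exists to pick out individual children whose values are unusual. It works only if crossing a limit carries roughly the same meaning for every child in it. If the usual level of a vital sign shifts between 6 and 17 years, a single cut-off sits at a different distance from the usual level in each age group. Where it is close, children cross it through ordinary visit-to-visit variation. Where it is far away, a real shift does not reach it.

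Both could occur in this trial. In the younger stratum the upper pulse and respiratory limits may be close to usual values, and the upper blood-pressure limits far from them. The at-risk rule then removes children who already exceed a limit at baseline, and it does so unevenly by age. Table 4 is the only categorical vital-sign analysis in the visible SAP, and it is planned without an age split, so a reader could not see any of this from the output.

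**Working it through.** The plan states no figure on this point to reproduce. The check takes the limits and visits from the documents and adds assumed distributions.

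**Inputs from the documents.** Limits: SAP Table 4. Post-baseline vital signs: Visits 5, 8 and 9 (SAP section 8.4). At-risk rule: SAP section 8.4.

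**Assumptions, not in either document.** Values are normal and recorded as whole numbers, so exceeding a limit L means exceeding L + 0.5. There is one baseline and three post-baseline readings with within-child correlation 0.3 to 0.7. There is no drug effect unless stated. Means and SDs are as given below.

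**Respiratory rate above 20, ages 6-11, SD 2.5.** The share excluded at baseline is 1 − Φ((20.5 − mean)/2.5). The share newly flagged is the simulated proportion of at-risk children above the limit at any of the three later visits.

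| Assumed mean | z | Excluded at baseline | Flagged among those at risk |
|---|---|---|---|
| 16 | 1.8 | 4% | 6% to 9% |
| 17 | 1.4 | 8% | 11% to 18% |
| 18 | 1.0 | 16% | 19% to 32% |
| 21 | −0.2 | 58% | 52% to 79% |

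The lower end of each range belongs to correlation 0.7 and the upper end to 0.3. Over means of 16 to 21, exclusion runs from 4% to 58% and new flags from about 6% to 79%.

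**Pulse above 100, SD 11, single reading.**
- Ages 6-11, mean 82 to 90: z = (100.5 − 82)/11 = 1.68 to (100.5 − 90)/11 = 0.95, so 5% to 17% exceed the limit.
- Ages 12-17, mean 74 to 82: z = 2.41 to 1.68, so 1% to 5% exceed it.

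**Systolic pressure, ages 6-8, mean 96 to 104, SD 10, single reading.**
- Upper limit: (140.5 − 104)/10 = 3.65 to (140.5 − 96)/10 = 4.45 SD above the mean.
- Lower limit: (89.5 − 96)/10 = −0.65 to (89.5 − 104)/10 = −1.45, so 26% to 7% of readings fall below 90.

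**Sensitivity of the upper systolic limit (correlation 0.5).** The shifts are illustrative. Each is applied to every child after baseline.

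| Shift | At-risk children ever above 140 | Ever above a limit 2 SD over the age mean |
|---|---|---|
| none | under 0.1% | about 4.5% |
| +10 mmHg | 0.1% to 1.1% | about 29% |
| +15 mmHg | 0.5% to 4% | about 51% |

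Under these assumptions the fixed limit barely moves under a shift that an age-scaled limit would show clearly.

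**The case against.** The strongest reply is that the documents contain no paediatric reference values. They do not call the limits adult limits, and they do not say what is usual or high at any age. A reader might infer that the table flags normal young children and misses clinically high blood pressure. Neither can be established from these documents, and both depend on where the usual values lie. The respiratory result shows how much: at an assumed mean of 16 to 17 the new-flag rate is only 6% to 18%. This part of the reply stands, and it is why the size is given as a range under stated assumptions.

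A reader might also infer that the arms would be compared unfairly, or that the table cannot be interpreted at all. The documents point the other way:

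- Allocation is 1:1 and stratified by the same two age groups, so age-driven flags should be roughly balanced between arms.
- Baseline is taken before the first dose (SAP section 4.2), so treatment cannot affect who is excluded at baseline.
- Actual values and changes from baseline are summarized at each time point without reference to Table 4, and would show an average shift. Listings, adverse-event tables and the data monitoring committee's unblinded review add further cover.

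Nor does the at-risk rule simply make matters worse. It reduces flags unrelated to drug. At a respiratory mean of 18, 28% to 36% of all children would be flagged at some visit, against 19% to 32% of those at risk under the rule. Its cost is a smaller denominator that is selected by age.

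Finally, the trial is exploratory and the table is descriptive. No dosing or withdrawal rule uses it. That limits the weight of the point but does not remove it: balance between arms does not restore a signal that a limit cannot register, and averages can hide the individual outliers that this table is meant to find.

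**Conclusion.** The point holds in a limited form. Four vital signs are judged against one absolute limit set across ages 6 to 17, with no age band, no stated source and no visible display by age. If usual values change with age, the cost is noise, an at-risk set selected by age, and low sensitivity in younger children. It is not bias between arms.

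Under the stated assumptions, 4% to 58% of children aged 6-11 would leave the respiratory-rate denominator, and about 6% to 79% of the rest would be flagged with no drug effect. The upper systolic limit would lie about 4 SD above the mean at 6-8 years. These figures rest on assumed means, SDs and correlations. The width of the respiratory range reflects mainly the assumed mean. No figure for the whole table is possible, because the share of children aged 6-11 is not known in advance.

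This is worth correcting before unblinding, as an improvement to a safety display. It does not affect efficacy conclusions and concerns analysis flags only, not how any child is managed.

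**What to change.** Before unblinding, amend SAP section 8.4 and Table 4 as follows:

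1. Replace the single pulse, respiratory-rate, systolic and diastolic limits with age-banded limits from a cited paediatric reference. For blood pressure, use limits by age, sex and height.
2. Keep the L/H/HH layout, the at-risk rule and the relative weight row.
3. Show the marked-abnormality table for the 6-11 and 12-17 strata as well as overall, with the number at risk for each parameter in each stratum.

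No new data are needed. Date of birth and sex are recorded (Protocol section 9.1.3), and height is measured once, at Visit 1 (Protocol section 9.1.6 and Appendix 1).

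The cost is revised SAP wording and a lookup table in the programming. A small downside is that the limits would differ from any common table the sponsor uses in other reports. If the sponsor prefers common limits, the minimum is to state their source, justify their use across 6 to 17 years, and add the display by stratum. That would show the age pattern but would not restore sensitivity at the upper blood-pressure limits.

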8.5 Physical Examination

Physical examination findings for Visit 1 and Visit 8 EoT/WD, will be summarized as recorded. Height, weight, and BMI will be summarized as continuous variables. Categories of findings (normal, abnormal, not evaluated) on physical examination will be summarized as frequency and percentages.

8.6 12-lead ECG

A 12-lead ECG will be performed at Visit 1 and Visit 8 EoT/WD. Summaries of actual values and changes from baseline will be presented.

Marked abnormalities will be summarized, using a similar approach as described in Section 8.4.

Table 3 Marked abnormalities for 12-lead ECG

Parameter (unit)	Observed Values
QTcF (msec)	> 450
	> 480
	> 500

8.7 C-SSRS

The C-SSRS is a suicide risk assessment performed by the investigator at Visit 1 (Screening), Visit 2, Visit 5, Visit 7, Visit 8 EoT/WD, and Visit 9.

The number and percent of subjects with suicidal ideation by category, suicidal behavior by category and/or self-injurious behavior without suicidal intent will be tabulated. Percentages will be based on the number of subjects with at least one post-baseline C-SSRS assessment.

Shift from baseline showing any change in suicidal ideation and suicidal behavior will be provided. Subjects will be summarized under the worst of the following three categories: 1) No suicidal ideation of behavior; 2) suicidal ideation only; 3) suicidal ideation and behavior.

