9.1.11.10 Columbia-Suicide Severity Rating Scale

The C-SSRS supports suicide risk assessment through a series of simple, plain-language questions which answers help users identify whether someone is at risk for suicide, assess the severity and immediacy of that risk, and gauge the level of support that the person needs. It is completed as an interview covering whether and when they have thought about suicide (ideation), what actions they have taken, and when, to prepare for suicide and whether and when they attempted suicide or began a suicide attempt that was either interrupted by another person or stopped of their own volition.

Suicidality will be assessed by using the C-SSRS via interview with the patient or, if the patient is not being cooperative, interview with the patient's caregiver assistance. If the interview is carried out with the caregiver this must be recorded and justified in the patient notes.

It is expected that some patient may engage in non-suicidal self-harming behavior. Self-harming behavior is not per se an exclusion or withdrawal criteria unless it is carried out with suicidal intent. However, if an increase in non-suicidal self-harming behavior if observed this should be reported and an adverse event and the investigator should consider if it is safe for the patient to continue in the trial.

The C-SSRS is to be completed by the investigator or a delegate who has completed the C-SSRS training within the past 2 years or has continually administered the C-SSRS assessments throughout this trial since obtaining the training certificate.

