12.7 Follow-up Procedures for Adverse Events

The investigator may be asked to provide follow-up information to the GW PVD for any AEs reported or during the investigation of potential safety issues. Such requests for additional safety information may occur after a patient has finished a trial.

Additional information may also be requested by GW PVD if a patient experiences any adverse events that is considered an AESI, these include any events that may infer to hepatic enzymes increased, rash, pneumonia, cognitive disorders and self-injurious ideation or intentional self-injury.

AEs considered related to the IMP by the investigator or the sponsor should be followed up until resolution or the event is considered stable.

It will be left to the investigator's clinical judgment whether an AE is of sufficient severity to require the patient's removal from treatment. A patient may also voluntarily withdraw from treatment due to what he or she perceives as an intolerable AE. Further details of withdrawal are presented in Section 10. If either of these occurs, the patient must undergo an end of treatment assessment and be given appropriate care under medical supervision until symptoms cease or the condition becomes stable. If a safety concern is identified following withdrawal of a patient, GW may contact the investigator for additional follow-up information.

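### Within the C-SSRS analysis, non-suicidal self-injury has no baseline reference, so habitual and new cases are counted together

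*SAP*

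**What the plan says.** SAP 8.7 plans two C-SSRS displays.

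- **Tabulation.** Suicidal ideation by category is counted, and "suicidal behavior by category and/or self-injurious behavior without suicidal intent will be tabulated". The denominator is broad: "Percentages will be based on the number of subjects with at least one post-baseline C-SSRS assessment". Nothing separates patients who already had the behavior before dosing.
- **Shift.** "Shift from baseline showing any change in suicidal ideation and suicidal behavior will be provided". Each patient is placed in the worst of three categories: "1) No suicidal ideation of behavior; 2) suicidal ideation only; 3) suicidal ideation and behavior". None of them is for self-injury without suicidal intent.

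The scale is "performed by the investigator at Visit 1 (Screening), Visit 2, Visit 5, Visit 7, Visit 8 EoT/WD, and Visit 9", so there are two assessments before the first dose.

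Protocol 9.1.11.10 says: "It is expected that some patient may engage in non-suicidal self-harming behavior". It adds that such behavior does not by itself exclude or withdraw a patient, and that an observed increase is to be reported as an adverse event. Protocol 12.7 lists the events that may be handled as AESIs: "hepatic enzymes increased, rash, pneumonia, cognitive disorders and self-injurious ideation or intentional self-injury".

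For vital signs, SAP 8.4 uses an at-risk denominator: "those not meeting the criterion at baseline (or having a missing baseline value) and having at least one post-baseline value".

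**The concern.** A child who begins to self-injure on treatment, without suicidal intent, is in the first shift category before and after dosing and shows no shift. In the tabulation, that child looks the same as one who has self-injured for years. The table therefore cannot tell new from pre-existing self-injury.

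The gap falls on the item where pre-existing cases are most to be expected. Protocol 6.2.22 excludes any lifetime suicidal behavior and recent ideation of type 4 or 5, so eligibility largely clears the items that do get a baseline comparison. Self-injury is not cleared. Protocol 3.3.1 counts it among the commonest conditions associated with ASD.

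Two things are at stake in this table: sensitivity to a difference in new onset, and the ability to see whether the arms differed by chance at entry.

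**Working it through.** The documents give no figure for self-injury, so there is none to reproduce. The sample size follows from Protocol 13.1: 144/(1-0.10) = 160 randomized, or 80 per arm.

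**Formula.** Let b be the share already self-injuring at baseline, all of whom continue, and p the onset rate among the rest. Then:

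- rate in an arm = b + (1-b)p
- all-patient risk difference = (1-b)(p1-p0)
- number at risk per arm = 80(1-b)

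If only a share s of habitual cases continues, and s is the same in both arms, the rate becomes bs + (1-b)p and the risk difference is unchanged. Full persistence is therefore not needed for the factor (1-b).

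**Assumptions, none from the documents.** b = 20%, 30% or 40%; onset 20% versus 5% or 15% versus 5%. For example, at b = 30% and onset 20% versus 5%, the rates are 0.30 + 0.70×0.20 = 44.0% and 0.30 + 0.70×0.05 = 33.5%.

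| Onset | b | Planned table | RD (points) | RR | At risk per arm | RD (points) | RR |
|---|---|---|---|---|---|---|---|
| 20% v 5% | 20% | 36.0% v 24.0% | 12.0 | 1.50 | 64 | 15 | 4.0 |
| 20% v 5% | 30% | 44.0% v 33.5% | 10.5 | 1.31 | 56 | 15 | 4.0 |
| 20% v 5% | 40% | 52.0% v 43.0% | 9.0 | 1.21 | 48 | 15 | 4.0 |
| 15% v 5% | 20% | 32.0% v 24.0% | 8.0 | 1.33 | 64 | 10 | 3.0 |
| 15% v 5% | 30% | 40.5% v 33.5% | 7.0 | 1.21 | 56 | 10 | 3.0 |
| 15% v 5% | 40% | 49.0% v 43.0% | 6.0 | 1.14 | 48 | 10 | 3.0 |

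The last two columns are for patients without the behavior at baseline.

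**Precision at b = 30%, onset 20% versus 5%.** Habitual cases add noise as well as shrinking the difference.

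- Planned table: SE = √(0.335×0.665/80 + 0.44×0.56/80) = 7.7 points, so 10.5 ± 15.0.
- At risk only: SE = √(0.05×0.95/56 + 0.20×0.80/56) = 6.1 points, so 15 ± 11.9.

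**Sensitivity gauge.** SAP 8.7 plans no test, so this is only a yardstick: the chance of two-sided Fisher p<0.05 with 80 randomized per arm.

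| Onset | Group | b = 20% | b = 30% | b = 40% |
|---|---|---|---|---|
| 20% v 5% | Planned table | 31.8% | 22.1% | 15.9% |
| 20% v 5% | At risk only | 66.8% | 58.2% | 48.1% |
| 15% v 5% | Planned table | 15.7% | 11.5% | 8.5% |
| 15% v 5% | At risk only | 35.9% | 29.3% | 22.7% |

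A normal approximation for 20% versus 5% gives 38%, 27% and 21% against 73%, 67% and 61%. The levels are higher but the contrast is the same. With b = 0 there is no dilution.

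**Chance imbalance.** At b = 30%, the SE of the baseline difference between arms is √(2×0.30×0.70/80) = 7.2 points. An imbalance of that size would pass unseen into the planned percentages.

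**The case against.** The strongest objection is that the plan already has baseline-referenced views of this behavior. Much of that stands.

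- **Adverse events.** Protocol 9.1.11.10 makes an increase in self-harm reportable, and Protocol 12.5 calls for a new record when a pre-treatment event worsens after the first dose. SAP 8.2 counts as treatment-emergent only events that began or worsened after that dose, and it summarizes treatment-emergent AESIs. Stable habitual self-injury should not enter these tables. AEs are also reviewed at telephone Visits 3, 4, 6 and 10, when no C-SSRS is done.
- **ABC-I.** Protocol 3.3.1 assigns it to problem behaviors that include self-injury, and SAP 7.1.1 and 7.2.2 analyze its change from baseline with baseline in the model.

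A reader might infer that a drug effect on the special-interest harm itself is diluted. The documents do not support that: AESI status belongs to the adverse event route, which already separates new or worsened from habitual. A reader might also infer that new self-injury would be largely masked. Under the assumptions above, 60% to 80% of the risk difference survives.

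The other routes do not close the gap in 8.7. The AE route depends on someone noticing and reporting an increase, and AESI handling is optional under Protocol 9.1.13. The SAP's AESI cross-references point to Sections 8.1.3 and 8.1.2, although AESIs are in 8.2.1. ABC-I is a 15-item composite. The C-SSRS is the structured interview done in both arms at fixed visits.

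Three further limits stand. SAP 8.7 implies a post-baseline table through its denominator but does not say so outright, and the table shells are in a separate document. SAP 6 requires listings of recorded data, so a recorded baseline status would be visible patient by patient. The at-risk rule in 8.4 is a precedent in the same SAP, not a standard that 8.7 breaches.

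**Conclusion.** The point holds for the C-SSRS analysis only. As written, SAP 8.7 cannot separate new from pre-existing non-suicidal self-injury, and a new-onset risk difference shrinks by the factor (1-b) for any b above zero. The size cannot be fixed from the documents, because prevalence, onset rates and persistence are all assumed. An ABC-I score of at least 15 at entry does not establish self-injury.

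The mixing acts on both randomized arms alike, so it costs sensitivity and does not favor either arm. A chance imbalance at entry would, however, not show in the summary table. In an exploratory trial with descriptive safety reporting, this is a modest but worthwhile correction to the reporting.

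**What to change.** In SAP 8.7:

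1. Add non-suicidal self-injury (yes/no) to the shift from baseline to worst post-baseline value. Count it as present at baseline if recorded at either Visit 1 or Visit 2. SAP 4.2 takes the last pre-dose observation, normally Visit 2, and the documents give no recall period for this item; a short period could make a habitual case look new.
2. Report by arm the number and percentage with new onset among patients without the behavior before the first dose, with a descriptive risk difference and 95% CI.
3. Keep the existing all-patient tabulation.
4. State that worsening in patients already affected is assessed through adverse event reporting, because a yes/no shift cannot show greater frequency.

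The cost is a few lines of SAP text and one table block. It uses C-SSRS assessments already scheduled, provided the item is recorded before dosing. No visit, dose or clinical rule changes.
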